**Request for Expedited IRB Review Form attached**

**Human Subject Research:** Human subject research means research involving interaction or intervention with living human beings or access to identifiable private information of living human beings.

**Research Plan:** The information requested in the Research Plan is designed to provide the IRB with the necessary information such that it can make the federally required determinations codified at 38 CFR Part 16, 21 CFR Parts 50, 54, & 56, and 45 CFR Part 46

The **Research Plan** is to be written so that the non-scientist/non-medical members of the IRB can understand the research proposed. Define all abbreviations and terms that are not part of common language.

**Version Date:** This should be updated subsequently with every modification to any part of the Research Plan. Any modification to this document, no matter how minor, must be reviewed and approved by the IRB prior to implementation. The Research Plan will be stamped with the date of IRB approval

## Section 2 – Research Sites and Sponsor

5. Please list all Research Sites in addition to Louis Stokes Cleveland DVA Medical Center (LSCDVAMC); N/A

International studies when the PI is the Lead Investigator list the countries:

a. When study procedures including analysis of identifiable samples or data involving LSCDVAMC enrolled subjects will be conducted at any site other than the LSCDVAMC please provide the following:

Name and contact information for the site:

Describe the plan for communicating protocol amendments, reports of serious adverse events, reports of unanticipated problems involving risks to subjects or others, interim reports, and DSMB reports to external sites.

\* When the LSCDVAMC is considered the coordinating center and the PI the lead investigator on cooperative research or a multi-center trial contact AO/Research [[contact]](mailto:[contact]).

6. Sponsor or other Support (list industry sponsor, government support, etc.):

CAREER DEVELOPMENT AWARD, Department of Veterans Affairs, REHABILITATION RESEARCH & DEVELOPMENT. Award Number I01BX007080

## Section 3 – Research Design and Procedures

7. Definitions- Provide a list of all abbreviations and specialized terms to be used in this document and their definitions:

Abbreviations / Specialized Terms (Use the Enter key in this column to insert additional abbreviations and their definitions)	Definition
LSCDVAMC	Louis Stokes Cleveland DVA Medical Center
MS	multiple sclerosis
INO	internuclear ophthalmoplegia
MLF	medial longitudinal fasciculus
GEN	gaze-evoked nystagmus
CNS	central nervous system

8. Provide a BRIEF SUMMARY of the background for this research. DO NOT CUT and PASTE paragraphs that do NOT summarize the background.

- Include a critical evaluation of existing knowledge, and specifically identify the information gaps that your protocol is intended to fill.

- *Refer to appropriate citations in the scientific literature and include your references at the end of this section.*
- *Include the rationale for conducting the research at the VA.*

The study of eye movements is regarded as a powerful tool to investigate brain control of basic as well as high cognitive functions. As the neural substrate for eye movements is well understood, eye movement disorders are useful for localizing a pathological process within the central nervous system (CNS), and their study in the neuroscience allowed better understanding of both physiological and pathological conditions. The reason for extensive use of eye movements as a scientific tool, largely resides in their accessibility to measurement and analysis, as well as relatively easy reproducibility for experimental modeling. The proposed research aims at applying basic aspects of the control of eye movements to investigate gaze abnormalities, in particular concerning the coordination (conjugacy) of horizontal fast movements (saccades). The research strategy will be to use a typical multiple sclerosis (MS) ocular motor abnormality as a simple model to study the common but poorly understood complaint of fatigue in MS. The overall approach to the research here proposed stems from the well known history of basic and clinical investigations in the field of ocular motility, that has provided over the years insights into brain functioning and has translated into numerous treatments for patients with visual disability. The Daroff-Dell'Osso Ocular Motility Laboratory at the Louis Stokes DVA Medical Center, where the study will be conducted, has been a major contributor to vestibular and eye movement research for the last 30 years. The Daroff-Dell'Osso laboratory is a state-of-the-art eye movement center with top class equipment to conduct research in the field.

**9. Provide a BRIEF SUMMARY of the purpose and scientific rationale for this research. DO NOT CUT and PASTE paragraphs that do NOT summarize the purpose and scientific rationale.**

- *State clearly, in terms a non-scientist/non-medical person can comprehend, what you expect to learn from the study and the specific hypothesis (es) to be tested.*
- *The objectives should be stated in such a way that the reader can determine the appropriateness of the study design.*

With this proposal we expect to learn about mechanisms of motor fatigue in MS and provide a neurophysiological model for it, using a known eye movement abnormality often found in MS. More in general, we aim at studying the impact certain eye movement disorders have on often under-recognized visual dysfunction in patients affected. We will also evaluate the effect of a pharmacological treatment for a certain eye movement disorder in MS patients. Evidence suggests that primary motor fatigue, a highly disabling symptom in MS patients, originates within the CNS but a neurophysiological model to explain its underlying mechanisms is still lacking. As a consequence, medical treatment for fatigue are generally unsatisfactory. Moreover, fatigue remains difficult to objectify in the clinical settings as its assessment solely relies on subjective reports through standard questionnaires filled by patients (symptomatic fatigue). With this project, we propose a characteristic eye movement abnormality of eye coordination, internuclear ophthalmoparesis (INO), as a simple and accessible model for primary motor fatigue in MS. INO results from demyelination of a specific white matter tract in the brainstem (the medial longitudinal fasciculus, MLF) and is clinical evident with slowing of the adducting eye (i.e., the eye moving towards the nose) during horizontal gaze shifts, while the abducting eye (i.e., the eye moving away from the nose) is normal. Preliminary results in a small MS group show that patients with INO exhibit changes in ocular conjugacy (i.e., they show ocular motor fatigue) during a 10-minute recording of their fast eye movements (saccadic fatigue test), but normal subjects do not. In this respect, our hypotheses are: 1) ocular motor fatigue can complicate INO and is associated with worse scores of symptomatic fatigue than INO without ocular motor fatigue; 2) ocular motor fatigue is due to deterioration of neural conduction of the signal

needed to generate a saccade along the demyelinated MLF, which might be representative of a major component of primary motor fatigue in MS. The second part of the project concerns testing the effects of dalfampridine (a potassium channel blocker that enhances neural conduction along demyelinated axons) on MS-related INO with or without associated ocular motor fatigue. Visual dysfunction in MS patients with INO is a major cause of disability but no medical therapy is available. Our preliminary results document improved binocular conjugacy in three MS patients taking dalfampridine. In this respect, our hypotheses are: 1) dalfampridine improves visual performance in MS patients with INO and counteracts ocular motor fatigue; 2) improvement of INO and ocular motor fatigue with dalfampridine diminishes visual disability and improves quality of life in MS.

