**10. Describe the means of analyzing the data and evaluating the results.**

- *State the anticipated methods to be used for analysis and interpretation of the data.*
- *The methods must compliment the design of the study and the nature of the data which is being collected.*

This study investigates horizontal binocular conjugacy and ocular motor fatigue in MS patients with INO and the effects of treatment (dalfampridine) while eye movements are recorded during a 10-minute saccadic fatigue test. Patients will undergo clinical eye movement examination, visual performance assessment including reading acuity and speed, gait assessment, assessment of symptomatic fatigue, disability arising from visual dysfunction as well as quality of life, using available self-administered questionnaires and scales, and eye movement recording, before and after treatment. The treatment portion of the study will be conducted following a randomized, placebo-controlled, double-blind, crossover trial design, which will include a period of wash out of at least two weeks between treatment with dalfampridine and placebo. A minimum of 2 weeks is necessary to ensure wash out, however a washout period longer than 2 weeks will not confound the study results. There will be a total of 4 evaluations: at baseline, after washout, and after treatment with both dalfampridine and placebo. Subject participation will last an estimated 10-14 weeks. We anticipate most subjects will participate for 10 weeks, however due to unforeseen circumstances a subject may be unable to keep a scheduled appointment lengthening the overall time of their participation. In order to test our hypotheses, we use the following outcome measures, at time of each evaluation. A. Eye movement assessment: changes in binocular horizontal conjugacy at baseline and following the saccadic fatigue test using 1) abducting/adducting eye ratio for saccadic peak velocity (pulse size ratio); 2) time difference in occurrence of peak acceleration in the adducting vs. the abducting eye (pulse time delay). These measures of conjugacy of horizontal saccades are applied to data collected continuously throughout the fatigue test. B. Symptomatic fatigue assessment using 1) Fatigue Severity Scale (FSS); 2) Modified Fatigue Impact Scale (MFIS); C. Visual function assessment using 1) MNREAD acuity charts for reading acuity and speed; 2) King-Devick test for saccades performance; D. Gait assessment using 1) 25-foot Walk Test; 2) 6-minute Walk Test. E. Visual disability and quality of life assessment using 1) NEI-VFQ-25 and NOS; 2) MS Quality of Life Inventory. Standard statistical measures, such as paired dependent t-test, will be employed to determine significance of our results.

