**Eye Movement Recording.** Eye movements will be recorded using the EyeLink II system, (SR Research Ltd.). Subjects will sit in a 110-ft-lb vestibular chair (CNC Engineering), with head restrained, during all the experimental paradigms, and will follow a visual stimulus (a red laser spot) projected onto tangent screen. The EyeLink signal from each eye will be calibrated. We will obtain a baseline monocular and binocular viewing recording of eye movements then will perform the 10-minute saccadic fatigue test as previously described [Matta et al, 2009]. Patients will make horizontal saccades in response to 20-degree jumps, at 0.5 Hz across the midline (i.e., 1 saccade per second), of the visual target (laser spot).

At evaluations 2 and 4, patients will hold the am dose (dalfampridine or placebo), will undergo baseline eye movement recording, then will be recorded again 3 hours after taking their dose in the same session.

Visual function assessment using MNREAD acuity charts for reading acuity and speed and the King-Devick test for saccades performance. [name] will carry out these assessments.

Symptomatic fatigue assessment using self-administered questionnaires: the Fatigue Severity Scale (FSS) and the Modified Fatigue Impact Scale (MFIS).

Gait assessment using the 25-foot Walk Test and the 6-minute Walk Test. [name] will carry out these assessments.

Visual disability and quality of life assessment using the following self-administered scales: NEI-VFQ-25 and NOS; and the MS Quality of Life Inventory.

Renal function panel (serum) at baseline, to be repeated after 4 weeks and at the end of the trial. Phlebotomy will be performed by a lab technician in the blood work laboratory located in the first floor of the LSDVAMC.

Normal controls cohort (n=20).

**Enrollment.** [name] will be responsible for enrolling all age-matched normal controls for the study, including possibly residents, house staff and employees of the LSDVAMC and Case.

All controls will undergo clinical evaluation of vision and eye movements to confirm they have normal visual and ocular motor functions.

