**Eye Movement Recording (one session only).** Eye movements will be recorded using the EyeLink II system, (SR Research Ltd.). Normal controls will sit in a 110-ft-lb vestibular chair (CNC Engineering), with head restrained, during all the experimental paradigms, and will follow a visual stimulus (a red laser spot) projected onto tangent screen. The EyeLink signal from each eye will be calibrated. We will obtain a baseline monocular and binocular viewing recording of eye movements then will perform the 10-minute saccadic fatigue test as previously described [Matta et al, 2009]. Normal controls will make horizontal saccades in response to 20-degree jumps, at 0.5 Hz across the midline (i.e., 1 saccade per second), of the visual target (laser spot).

The table below summarizes the randomized, placebo-controlled, double-blind, crossover trial design, which will include a period of wash-out of at least two weeks between treatment with dalfampridine and placebo. In the event the washout period lasts longer than 2 weeks or a subject has difficulty keeping one of the study visits and needs to reschedule, subject participation would be greater than 10 weeks (estimated 10-14 weeks of participation).

[figure not shown]

Table. Flow diagram summarizing study design. Following enrollment and randomization subjects will undergo a total of 4 evaluations, each one consisting in: eye movement recording, symptomatic fatigue assessment, visual function assessment, gait assessment, visual disability and quality of life assessment. Renal function panel (serum) will be performed at baseline, to be repeated after 4 weeks and at the end of the trial. See text for details.

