#### 14. Will the research involve the following?

N/A    **Chart/Data Review**

Placebo Group	 No  Yes (describe): double blind placebo-controlled crossover trial of dalfampridine effects on INO and ocular motor fatigue in MS
Other Control Group	 No  Yes (describe): age matched for eye movement recording outcomes
Randomization	 No  Yes (describe): double blind placebo-controlled crossover trial of dalfampridine effects on INO and ocular motor fatigue in MS

**Deception**  No  Yes (describe):

**15. Does the research involve the use and/or disclosure of Individually Identifiable Health Information in any form or medium?**

No  Yes If yes, complete the required HIPAA Waiver/Authorization forms.

**16. Does the study include the administration of a study agent that does not require FDA approval and does not require an IND (e.g. vitamins, food supplements, isotope tracers, alternative medicines, etc.)?**

No  Yes -provide a detailed description of the procedures used to assure patient safety:

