#### **Section 4 – Subject Selection, Recruitment, and Vulnerable Populations**

**19. Anticipated duration of entire study reported in years: 3**

**20. Estimated number of subjects to be studied at the LSCDVAMC or charts/records to be reviewed.**

• *Provide answers for each cohort including normal controls; (patients, family members, treating physicians,):*

Patients: 30. Normal controls: 20.

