**30. Please list by bullet point inclusion/exclusion criteria for the study.**

- *Entry criteria should be as detailed as necessary to define the subject population(s) under study and reduce confounding design. Include precise criteria for age, gender, and other relevant factors.*
- *List specific exclusion criteria which could interfere with the study design or place a subject at risk during the study.*
- *Provide answers for each cohort, including normal controls.*

Patients cohort.

Inclusion criteria:

- Diagnosis of MS of any course and duration
- Evidence of mild to moderate INO (slowing of the adducting eye) on physical examination of saccadic speed, whether INO is unilateral or bilateral, symmetrical or asymmetrical
- Medically stable conditions, ability to give informed consent and understand and cooperate with the testing

- Dalfampridine-naïve as well as history of taking dalfampridine in the past, whether there was benefit in gait impairment or not, after a washout period of at least 2 weeks.

Exclusion Criteria:

- Lack of evidence of INO (slowing of the adducting eye) on physical examination of saccadic speed
- Severe INO (i.e., exotropia in primary gaze) on physical examination
- Medically unstable conditions, inability to give informed consent and/or understand and cooperate with the testing
- History of side effects from dalfampridine
- History of seizures
- Moderate or severe renal failure, assessed by clearance of creatinine
- Pregnancy.

Normal controls cohort.

Inclusion criteria:

- Age 18-65
- Healthy with normal visual and ocular motor function

N/A Chart/data review

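### The plan names the MLF as the site of ocular motor fatigue, but no planned contrast is specific to the MLF, and the less affected saccade direction is not used as a within-patient control

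*Combined protocol and SAP*

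**What the plan says.** Item 9 states the hypothesis as "2) ocular motor fatigue is due to deterioration of neural conduction of the signal", continuing "needed to generate a saccade along the demyelinated MLF, which might be representative of a major component of primary motor fatigue in MS". The preliminary support it cites is that patients with INO changed over the 10-minute test and normal subjects did not.

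- **Comparison group.** Apart from placebo, item 14 lists one control group, "age matched for eye movement recording outcomes". Item 20 gives the sizes: "Patients: 30. Normal controls: 20". Item 13 has the controls recorded in a single session. There is no group with MS but without INO.
- **Patients.** Item 30 admits mild to moderate INO "whether INO is unilateral or bilateral, symmetrical or asymmetrical".
- **Recording.** Item 13 calibrates the signal from each eye and moves the target back and forth across the midline, so saccades are made both ways, one per second.
- **Measures.** Item 10 defines pulse size ratio and pulse time delay, each comparing the abducting with the adducting eye. It adds: "These measures of conjugacy of horizontal saccades are applied to data collected continuously throughout the fatigue test".
- **Analysis.** The only test named in item 10 is a paired t-test. The plan does not say which direction is analysed, how two directions are combined, or how laterality of INO enters.

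**The concern.** The hypothesis makes a claim about location: the fatigue arises in one tract. A difference between INO patients and healthy volunteers cannot support that alone, because the groups differ in having MS at all. Effort, attention, general MS fatigue and MLF conduction would all be candidate explanations.

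In unilateral INO, saccades in one direction depend on the damaged MLF and saccades in the other do not. In asymmetrical INO, one direction depends on the worse-damaged side. Comparing the two directions within the same patient and the same 10 minutes holds effort, attention, general fatigue and time on task constant. The planned recordings contain this comparison, but the plan does not use it.

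At stake is how a positive result may be read. As planned, it would show that MS patients with INO lose conjugacy during the test. It would not show that the MLF is where this happens, and the proposed model of primary motor fatigue rests on that step.

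**Working it through.** **1. What each planned contrast can separate**

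| Contrast | Removes | Leaves open |
|---|---|---|
| Patients vs healthy controls (items 13, 14, 20) | Change that healthy people also show on the test | Anything that comes with MS, in the MLF or elsewhere |
| Abducting vs adducting eye in the same saccade (item 10) | Change common to both eyes | Any other patient-specific change that affects the eyes unequally |
| Dalfampridine vs placebo (item 9) | Stable patient characteristics | Which demyelinated pathway responds, since the drug is described as acting on demyelinated axons in general |
| Affected vs less affected direction (not planned) | Effort, attention, general fatigue, time on task | Undetected damage on the better side, which would shrink the contrast |

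**2. Are the data there?** One saccade per second for 10 minutes is 10 × 60 = 600 saccades, about 600 / 2 = 300 per direction in each test.

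**3. The plan's own sample sizes.** Item 11 gives 9 patients for an effect size of 0.93 and 17 for 0.63, at power 0.80 and alpha 0.05, with sidedness not stated. A one-sided paired t-test gives 9 for 0.93 (power 0.82 at 9) and 18 for 0.63 (power 0.80, rounded, at 17). Both figures are therefore reproduced, within one patient, as one-sided tests. Two-sided, the numbers would be 12 and 22.

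**4. Power of the missing contrast.** Let m be the number of patients with unilateral or asymmetrical INO, and d the mean between-direction difference in 10-minute change divided by its SD. Neither is in the documents. For illustration, d is set to the item 11 values. The test is a paired t-test with m − 1 degrees of freedom, noncentrality d√m and two-sided alpha 0.05.

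| m | Critical t | d√m (0.63 / 0.93) | Power (0.63 / 0.93) |
|---|---|---|---|
| 5 | 2.776 | 1.41 / 2.08 | 0.19 / 0.36 |
| 10 | 2.262 | 1.99 / 2.94 | 0.43 / 0.74 |
| 22 | 2.080 | 2.95 / 4.36 | 0.80 / 0.99 |

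If all 30 patients were usable, power would be 0.92 or above 0.99.

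**5. What the handling of direction could do to the drug comparison.** Take 30 patients and the item 11 drug effect of 0.5 as the effect in an affected direction. Assume bilateral patients have that effect in both directions, and that a share u of patients is unilateral with none in the unaffected direction. Let ρ be the correlation between directions. Averaging the two gives

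d(average) = 0.5 × (1 − u/2) / √((1 + ρ)/2).

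Example: u = 0.5, ρ = 0.5 gives 0.5 × 0.75 / √0.75 = 0.433, power 0.63. Analysing the affected direction alone gives power 0.75.

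| ρ | u = 0 | 0.25 | 0.50 | 0.75 |
|---|---|---|---|---|
| 1 | 0.75 | 0.64 | 0.51 | 0.38 |
| 0.5 | 0.86 | 0.76 | 0.63 | 0.48 |
| 0 | 0.96 | 0.91 | 0.80 | 0.65 |

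Averaging can gain or lose. The documents give neither u nor ρ.

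**The case against.** The strongest reply is that the hypothesis does not rest on healthy controls alone. Both outcome measures use the abducting eye as a reference within the same saccade, and item 9 describes that eye as normal in INO. Slowing from poor effort or general fatigue that affects both eyes alike is at least partly cancelled. The crossover adds a second within-patient probe of conduction. This stands: a reader who infers that healthy controls are the only contrast bearing on the hypothesis goes too far. Neither feature, however, identifies the MLF as the site.

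A reader might also infer from item 10 that left and right saccades are pooled, and that the drug comparison loses power as a result. The documents do not support this. The sentence about continuous data describes coverage over time and is silent on direction. Item 13 refers to a published description of the fatigue test, which may or may not treat directions separately. Step 5 shows that pooling need not lose power.

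Two cautions about the remedy also stand. Choosing the worse direction from the same recording that is then analysed invites regression to the mean. And with few usable patients the contrast could be badly underpowered. Finally, item 9 words its extension to MS fatigue in general cautiously. That does not soften the causal statement about the MLF itself.

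**Conclusion.** The point holds as a gap in specificity. The hypothesis places the fatigue in the MLF, no planned contrast is specific to the MLF, and a within-patient contrast that is more specific lies unused in the planned recordings. No figure in the plan is contradicted.

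How much the added contrast can show depends on two unknowns: the number of patients with unilateral or asymmetrical INO, and the size of the between-direction difference. At the plan's effect sizes, power of 0.80 needs 22 patients (0.63) or 12 patients (0.93), out of 30. If the less affected direction also tires, the difference would be smaller. The contrast is therefore supportive, and a null result with few patients would not refute the hypothesis.

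For the drug comparison, all that can be said is that the handling of direction is unspecified and should not be left open until results are seen.

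**What to change.** 1. Record at enrolment, from the clinical examination, whether INO is unilateral, asymmetrical or symmetrical, and which direction is affected or worse. Do not designate the direction from the recording being analysed.
2. Compute pulse size ratio and pulse time delay separately for rightward and leftward saccades.
3. For the MLF hypothesis, prespecify a paired comparison in patients with unilateral or asymmetrical INO: the change over the 10-minute test in the affected (or worse) direction minus that in the less affected direction. Label it supportive and report the number of patients with a confidence interval.
4. Keep the healthy controls to describe the normal range. Limit any statement that the MLF is the site to what the within-patient contrast shows.
5. For dalfampridine versus placebo, state in advance how the two directions are combined. Using one direction or both is a trade-off, so the single worse direction need not be imposed.

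**Cost.** Added analysis text and one item on the enrolment form, with no new patients, visits or recordings. The drawbacks are that symmetrical bilateral patients contribute little, that the usable number is unknown, and that a subclinical lesion on the better side would make the contrast conservative.

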
**11. Provide a BRIEF DESCRIPTION of how the estimated number of study subjects needed for this research was determined**

- *If this is a quantitative study provide the method of determining sample size estimates.*
- *If multiple studies are planned provide a power analysis or justification for each one.*

To determine the number of subjects needed for this study, we conducted a power analysis based on our preliminary data of increase in pulse size ratio and pulse time delay after the 10-minute fatigue test in two different sample populations of MS patients with INO. Based on a large effect size of 0.93, we found that we will need a sample size of 9 patients to reach a power of 0.80 (alpha 0.05) for the first outcome measure (pulse size ratio). Based on a moderately large effect size of 0.63, we found that we will need a sample size of 17 patients to reach a power of 0.80 (alpha 0.05) for the second outcome measure (pulse time delay). Because only one out of three patients showed clinically significant changes of pulse size ratio and pulse time delay after dalfampridine, while changes were subclinical in the other two patients, we were not able to provide a power analysis for the expected effects of dalfampridine in our trial. However, we found that for a clinically meaningful effect size of 0.5, with alpha of 0.05, we will need a sample size of 27 patients to yield a power of 0.85 [Norman et al., 2000]. Thus we aim at recruiting, studying and treating 30 patients.

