**40. Describe all procedures that minimize risks, please include study and standard of care procedures:**

We will not enroll subjects in which AMYRA is contraindicated: history of seizure, moderate or severe renal impairment, history of hypersensitivity to AMPYRA or similar compounds. To minimize possible side effects, subjects will be taking the FDA-recommended dose of AMPYRA (10 mg tablet twice daily), with doses taken approximately 12 hours apart and only taken whole. Subjects will be advised not to take double or extra doses if a dose is missed.

Since AMPYRA can cause side effects, especially seizures, in subjects with abnormal renal function, this will be checked through standard blood work at baseline, after 4 weeks and at the end of the study.

We will keep all eye movement recordings under 30 minutes to minimize possible discomfort.

If subjects do not wish to answer a question in a questionnaire, they may skip it and go to the next question.

To ensure confidentiality of patient's records, we will keep all records on a password-protected computer in Room BC 300c in the Daroff-Dell'Osso Ocular Motility Laboratory. This computer has an encryption firewall. Paper records will also be kept in a locked cabinet in Room BC 300c; the keys to the room and cabinet will be retained by [name]. Each patient will be assigned a number based on the hour and date of their study. The key to the numbers/patients will be stored in [name] password-protected computer and in the memories of each patient and [name]. At the end of the study, all data will be stored on a password-protected CD, kept in [name] locked cabinet and will be retained indefinitely.

**41. Describe alternative procedures or course of treatment, if any, which might be advantageous to the subject. State if no alternatives exist or if this is not a treatment study.**

AMPYRA is potentially available to subjects outside of the research study with the FDA-approved indication for gait impairment. Because of the nature of this research the only alternative is to not participate in this study. Currently, there are no other approved treatment/drugs for the treatment of INO.

**Minimal Risk:** Minimal risk means that the risks of harm anticipated in the proposed research are not greater, considering probability and magnitude, than those ordinarily encountered in daily life or during the performance of routine physical or psychological examinations or tests.

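### Hypothesis 2 makes eye-movement improvement the cause of less visual disability and better quality of life, but the only named analysis cannot link these outcomes

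*Combined protocol and SAP*

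**What the plan says.** Section 3, item 9 gives two hypotheses for the treatment part. The first is a plain drug effect: "dalfampridine improves visual performance in MS patients with INO and counteracts ocular motor fatigue". The second has a different subject: "improvement of INO and ocular motor fatigue with dalfampridine diminishes visual disability and improves quality of life in MS". There the drug acts through the eye-movement improvement, and that improvement is said to produce the benefit.

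Item 10 lists the outcomes taken at each evaluation. Besides the eye-movement measures (pulse size ratio and pulse time delay), they include "D. Gait assessment using 1) 25-foot Walk Test; 2) 6-minute Walk Test" and "E. Visual disability and quality of life assessment using 1) NEI-VFQ-25 and NOS; 2) MS Quality of Life Inventory". On analysis it says: "Standard statistical measures, such as paired dependent t-test, will be employed to determine significance of our results". No correlation, regression or adjustment for gait is named, and no criterion says what result would support hypothesis 2. Item 11 sizes no analysis of association.

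Section 5, item 41 records that "AMPYRA is potentially available to subjects outside of the research study with the FDA-approved indication for gait impairment". Section 4, item 30 admits patients with a "history of taking dalfampridine in the past, whether there was benefit in gait impairment or not", provided they have washed out.

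**The concern.** A paired comparison of drug with placebo estimates one mean difference for one outcome. A significant result for pulse size ratio and another for a disability or quality-of-life scale are two drug effects. They do not show whether the patients whose INO improved are the ones whose scale scores improved, and still less whether the first change caused the second.

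For general quality of life, the documents themselves supply another explanation. The drug is approved for gait impairment, so the MS Quality of Life Inventory could improve because walking improved, with no contribution from INO. The plan measures gait but gives it no role in the analysis.

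At stake is the wording of a main conclusion. With no criterion for hypothesis 2, a pair of significant tests could be reported as confirming the pathway.

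**Working it through.** **1. Hypotheses against methods.** Hypothesis 1 states that the drug changes visual performance and ocular motor fatigue; a paired drug-placebo comparison addresses it. Hypothesis 2 states that the INO change leads to changes in disability and quality of life. That is a statement about how two changes relate within patients, and nothing in items 10 or 11 estimates such a relation.

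**2. The plan's own sizing figure.** Item 11 gives 27 patients "for a clinically meaningful effect size of 0.5, with alpha of 0.05", with power 0.85. Sidedness is not stated. For a paired design, n = ((z_alpha + z_beta)/d)².
- One-sided: ((1.645 + 1.036)/0.5)² = 28.8, so 29. This is the closest match to 27.
- Two-sided: ((1.960 + 1.036)/0.5)² = 35.9, so 36.
- Exact paired t: 31 one-sided, 38 two-sided.

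The figure of 27 is therefore matched only approximately, by the one-sided normal formula. The present point does not depend on it. It matters here only as the source of d = 0.5 and of the 30 patients.

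**3. How often both tests are significant with no link (illustration).** Assumptions that are not in the documents: the 0.5 applies to both an eye-movement measure and a quality-of-life scale, in SD of the paired difference, and the two changes are independent across patients.
- Two-sided paired t power at d = 0.5, n = 30: 0.754. Both significant: 0.754² = 0.568, about 57%. One-sided: 0.848² = 0.720, about 72%.
- n = 27, two-sided: 0.706² = 0.498, about 50%.
- Quality-of-life effect 0.3, n = 30, two-sided: 0.754 × 0.355 = 0.268, about 27%.
- Quality-of-life effect 0.2, n = 30, two-sided: 0.754 × 0.185 = 0.140, about 14%.

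A simulation of 40,000 trials, with INO change and quality-of-life change unrelated, gave 57.0% and 26.7% for the 0.5 and 0.3 cases at n = 30. A direct two-sided test of the correlation was falsely significant in 5.0% and 5.1%.

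**4. What an association analysis could detect.** By Fisher's z, the correlation with 80% power is tanh((1.960 + 0.842)/√(n − 3)).
- n = 30: tanh(2.802/√27) = 0.49.
- n = 27: tanh(2.802/√24) = 0.52.
- n = 30 with one covariate, such as sequence: tanh(2.802/√26) = 0.50.

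Simulated power at n = 30 is 37% for r = 0.3 and 61% for r = 0.4.

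**5. Why sequence must be in the model.** Suppose a period effect shifts each patient's drug-minus-placebo difference by +p in one sequence and −p in the other, in SD of the paired difference, on both outcomes. With equal sequences this adds p² to each variance and p² to the covariance. Two unrelated changes then have an expected correlation of about p²/(1 + p²).
- p = 0.3: 0.09/1.09 = 0.08.
- p = 0.5: 0.25/1.25 = 0.20.
- p = 0.8: 0.64/1.64 = 0.39.

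A correlation of raw differences could therefore show a link that is only a period effect. Adjusting for sequence removes this.

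**The case against.** Item 9 asks for a brief lay summary, and the words 'such as' in item 10 leave other methods open. The plan thus omits a linking analysis and does not rule one out. That stands. However, an analysis chosen after the data are seen is not pre-specified, so the gap remains.

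A reader might infer that the trial will treat two significant tests as proof of hypothesis 2. The documents do not say so. They give no decision rule, so the misreading is a risk and not a planned step.

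A reader might also infer that walking could explain every benefit. The documents support this only for general quality of life. Hypothesis 2 also covers visual disability, and nothing in the plan suggests that better walking would move the vision-specific NEI-VFQ-25 or NOS. For those scales the narrower point remains: separate tests do not connect the changes.

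The 57% could be mistaken for a false-positive rate. It is joint power to find two effects that are real in the assumed scenario. Both tests would be right, and only a causal reading of them would be wrong. The figure also falls quickly when the assumed quality-of-life effect is smaller.

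Finally, an association in 30 patients is weak evidence and cannot establish a causal pathway. This is correct. It is a reason to reword the hypothesis first and to treat any association as exploratory.

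**Conclusion.** The point holds as a gap between a hypothesis and its analysis. As written, the plan can support a drug effect on each outcome but cannot support the claim that improvement in INO and ocular motor fatigue is what reduces visual disability or improves quality of life. This conclusion follows from the text and rests on no figure. The 57% (27% with a quality-of-life effect of 0.3 SD) is illustrative and depends on assumed effect sizes, independent changes, two-sided tests and 30 complete patients.

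It would go too far to say that the trial is invalid. The randomised, masked crossover comparison of drug with placebo is untouched. What needs to change is the interpretation of one hypothesis, at little cost.

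**What to change.** 1. Reword hypothesis 2 so that the drug-placebo comparisons support only a statement that dalfampridine reduces visual disability and improves quality of life.

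2. Pre-specify one exploratory association analysis. Regress each patient's drug-minus-placebo change in NEI-VFQ-25 on the corresponding change in pulse size ratio, with treatment sequence in the model. Do the same, separately, for the MS Quality of Life Inventory, and repeat that model with change in 25-foot walk time as a covariate.

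3. State in advance which eye-movement recording is used, since item 13 has both a pre-dose and a 3-hour post-dose recording at evaluations 2 and 4. State also how a single value per patient is formed, since item 30 allows bilateral and asymmetrical INO.

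4. Report the partial correlation with its 95% confidence interval, as association only. Label pulse time delay, NOS and other pairings as exploratory, so that several measures and scales do not become a search for one significant result. State that 30 patients give 80% power only for r of about 0.49 (0.50 after adjusting for sequence), so a null result would say little.

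The cost is a few analyses on data already planned at every evaluation, low power for the association, and a more modest claim. No new visits, measurements or patients are needed.
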